5.13.2 Specific supportive care guidelines for pralatrexate

5.13.2.1 Leucovorin

Mucositis is the most frequent and treatment-limiting adverse event (AE) associated with the administration of pralatrexate. Leucovorin (*d,l*-folinic acid) is a reduced form of a racemic mixture of diasterioisomers of folic acid and is well-recognized and approved as rescue therapy for high-dose methotrexate (MTX) therapy, mitigating gastrointestinal lining and bone marrow cell toxicity [3]. It is also indicated to treat MTX or other folic acid antagonist overdose and is used in combination with fluorouracil to treat cancer of the colon. Leucovorin is approved as an antidote for the toxicity from folic acid antagonists, including pralatrexate. In the present study it is thus used to prevent or reduce mucositis resulting from pralatrexate treatment.

Leucovorin (25 mg tablets) will be administered orally three times daily (every 8 hours) for 2 days for a total of 6 doses (150 mg cumulative weekly dose) beginning 24h (+/- 2h) after each dose of pralatrexate is administered.

The patient will be instructed to take the first dose of leucovorin 24 hours (± 2 hours) after the administration of pralatrexate, and to continue to take the leucovorin three times daily (every 8 hours) for 2 days. At each weekly treatment visit, the patient will be asked whether they have taken leucovorin as instructed and will be supplied with a prescription to obtain additional doses.

5.13.2.2 Folic Acid supplementation/Premedication (Standard of care for pralatrexate therapy)

Folic acid (1 mg orally, once daily) supplementation is to begin within 10 days (as early as possible) prior to the first dose of pralatrexate administration (per pralatrexate product insert). However, if folic acid was not taken but MMA (methylmalonic acid) and HCY (homocysteine) levels were checked and are in normal range at screening, the investigator can decide to start study therapy immediately. Administration should continue during the full course of pralatrexate therapy and for 30 days after the last dose of pralatrexate.

5.13.2.3 Vitamin B12 supplementation/Premedication (Standard of care for pralatrexate therapy)

Vitamin B12 (1 mg IM) will be administered anytime within 10 weeks prior to initiation of pralatrexate (per pralatrexate product insert) and can be administered during screening, and will be administered every 3 cycles. Administration should continue during the full course of pralatrexate therapy and for 30 days after the last dose of pralatrexate.

5.13.3 General Supportive Care Guidelines

Participants should receive appropriate supportive care measures as deemed necessary by the treating investigator.

Suggested supportive care measures for the management of adverse events with potential immunologic etiology are outlined below. Where appropriate, these guidelines include the use of oral or intravenous treatment with corticosteroids as well as additional anti-inflammatory agents if symptoms do not improve with administration of corticosteroids. Note that several courses of steroid tapering may be necessary as symptoms may worsen when the steroid dose is decreased. For each disorder, attempts should be made to rule out other causes such as metastatic disease or bacterial or viral infection, which might require additional supportive care.

The treatment guidelines are intended to be applied when the investigator determines the events to be **related to pembrolizumab or pralatrexate** administration.

It may be necessary to perform conditional procedures such as bronchoscopy, endoscopy, or skin photography as part of evaluation of the event.

Myocarditis

- For suspected immune-mediated myocarditis, ensure adequate evaluation to exclude other etiologies.
- Administer corticosteroids as appropriate.

Pneumonitis

- Add prophylactic antibiotics for opportunistic infections in the case of prolonged steroid administration.

Grade 2

- Administer systemic corticosteroids.
- When symptoms improve to \leq Grade 1, steroid taper should be started and continued over no less than 4 weeks.

Grade 3 or 4

- Immediately treat with IV steroids.
- Administer additional anti-inflammatory measures, as needed.

Diarrhea/colitis

- All participants who experience diarrhea/colitis should be advised to drink liberal quantities of clear fluids. If sufficient oral fluid intake is not feasible, fluid and electrolytes should be substituted via IV infusion.
- For **Grade 2 or higher diarrhea**, consider GI consultation and endoscopy to confirm or rule out colitis.

Grade 2 diarrhea/colitis

- Administer oral corticosteroids.
- When symptoms improve to \leq Grade 1, steroid taper should be started and continued over no less than 4 weeks.

Grade 3 or 4 diarrhea/colitis

- IV steroids followed by high dose oral steroids
- When symptoms improve to \leq Grade 1, steroid taper should be started and continued over no less than 4 weeks.

Type 1 diabetes mellitus* OR \geq Grade 3 hyperglycemia**

- *if new onset, including diabetic ketoacidosis [DKA])
- **if associated with ketosis (ketonuria) or metabolic acidosis (DKA)

For T1DM or Grade 3-4 hyperglycemia

- Insulin replacement therapy is recommended.
- Evaluate patients with serum glucose and a metabolic panel, urine ketones, glycosylated hemoglobin, and C-peptide.

Hypophysitis

Grade 2 (i.e. symptomatic)

- Treat with corticosteroids.
- When symptoms improve to ≤ Grade 1, steroid taper should be started and continued over no less than 4 weeks.
- Replacement of appropriate hormones may be required as the steroid dose is tapered.

Grade 3 or 4

- Treat with an initial dose of IV corticosteroids followed by oral corticosteroids.
- When symptoms improve to ≤ Grade 1, steroid taper should be started and continued over no less than 4 weeks.
- Replacement of appropriate hormones may be required as the steroid dose is tapered.

Hyperthyroidism or hypothyroidism

Grade 2 Hyperthyroidism

- Non-selective beta-blockers (e.g. propranolol) are suggested as initial therapy.

Grade 3 or 4 Hyperthyroidism

- Treat with an initial dose of IV corticosteroid followed by oral corticosteroids.
- When symptoms improve to ≤ Grade 1, steroid taper should be started and continued over no less than 4 weeks.
- Replacement of appropriate hormones may be required as the steroid dose is tapered

Grades 2-4 Hypothyroidism

- Thyroid hormone replacement therapy, with levothyroxine or liothyroinine, is indicated per standard of care.

Hepatic

Grade 2

- Monitor liver function tests more frequently until returned to baseline values (consider weekly).
- Treat with IV or oral corticosteroids

Grade 3 or 4

- Treat with intravenous corticosteroids for 24 to 48 hours.
- When symptoms improve to ≤ Grade 1, steroid taper should be started and continued over no less than 4 weeks

Renal failure or nephritis

Grade 2

- Treat with corticosteroids

Grade 3 or 4

- Treat with systemic corticosteroids.
- When symptoms improve to ≤ Grade 1, steroid taper should be started and continued over no less than 4 weeks

Management of infusion reactions

- Pembrolizumab may cause severe or life threatening infusion-reactions including severe hypersensitivity or anaphylaxis. Signs and symptoms usually develop during or shortly after drug infusion and generally resolve completely within 24 hours of completion of infusion.

Dose modification and toxicity management guidelines on pembrolizumab associated infusion reaction are provided in Table 5.13.3.

Table 5.13.3 Pembrolizumab Infusion Reaction Dose modification and Treatment Guidelines

NCI CTCAE Grade	Treatment	Premedication at Subsequent Dosing
Grade 1 Mild reaction; infusion interruption not indicated; intervention not indicated	Increase monitoring of vital signs as medically indicated until the participant is deemed medically stable in the opinion of the investigator.	None
Grade 2 Requires therapy or infusion interruption but responds promptly to symptomatic treatment (e.g., antihistamines, NSAIDs, narcotics, IV fluids); prophylactic medications indicated for ≤24 hrs	
Stop Infusion.
 
Additional appropriate medical therapy may include but is not limited to:
 
IV fluids Antihistamines NSAIDs Acetaminophen Narcotics
 
Increase monitoring of vital signs as medically indicated until the participant is deemed medically stable in the opinion of the investigator.
 
If symptoms resolve within 1 hour of stopping drug infusion, the infusion may be restarted at 50% of the original infusion rate (e.g. from 100 mL/hr to 50 mL/hr). Otherwise dosing will be held until symptoms resolve and the participant should be premedicated for the next scheduled dose.
 
Participants who develop Grade 2 toxicity despite adequate premedication should be permanently discontinued from further study drug treatment
	
Participant may be premedicated 1.5h (± 30 minutes) prior to infusion of pembrolizumab with:
 
Diphenhydramine 50 mg po (or equivalent dose of antihistamine).
 
Acetaminophen 500-1000 mg po (or equivalent dose of analgesic).

Grades 3 or 4	Stop Infusion. Additional appropriate medical therapy may include but is not limited to: Epinephrine** IV fluids Antihistamines NSAIDs Acetaminophen Narcotics Oxygen Pressors Corticosteroids Increase monitoring of vital signs as medically indicated until the participant is deemed medically stable in the opinion of the investigator. Hospitalization may be indicated. **In cases of anaphylaxis, epinephrine should be used immediately. Participant is permanently discontinued from further study drug treatment.	No subsequent dosing
Appropriate resuscitation equipment should be available at the bedside and a physician readily available during the period of drug administration. For further information, please refer to the Common Terminology Criteria for Adverse Events v5.0 (CTCAE) at http://ctep.cancer.gov		

5.13.4 Other Considerations

Refer to [Appendix E](#) for contraception related guidance.

6.0 ANTICIPATED TOXICITIES & DOSE MODIFICATION/ DELAY GUIDELINES

6.1 Anticipated Toxicities

6.1.1 Pembrolizumab

Per the IB the expected toxicities for pembrolizumab are as follows (asterisk signifies ≥ 10%; no asterisk signifies 1-10%, † signifies < 1%, and ^ signifies unknown frequency):

Blood and lymphatic system disorders (includes investigations)	Anemia, neutropenia†, thrombocytopenia†, leukopenia†, lymphopenia†, eosinophilia†, hemolytic anemia†, immune thrombocytopenic purpura†
Cardiac	Myocarditis †
Endocrine	Hyperthyroidism, hypothyroidism, hypophysitis †, adrenal insufficiency †, thyroiditis †
Eye	Uveitis †, dry eye †, Vogt-Koyanagi-Harada disease ^
Gastrointestinal	Diarrhea*, nausea *, abdominal pain, vomiting, colitis, constipation, dry mouth, pancreatitis †, small intestine perforation †
General Disorders and Administration Site	Fatigue *, asthenia, edema, pyrexia, influenza-like illness, chills
Hepatobiliary	Hepatitis †, sclerosing cholangitis ^
Immune system	Infusion related reactions, severe infusion reactions †, sarcoidosis †, solid organ transplant rejection ^, GvHD (potential risk), haemophagocytic lymphohistiocytosis †
Investigations (excluding hematologic)	AST/ALT increased, blood alkaline phosphatase increased, blood creatinine increased, low sodium levels†, low potassium levels†, low calcium levels†, blood bilirubin increased†, amylase increased†, increased calcium †
Metabolism and Nutrition	Decreased appetite, type 1 diabetes mellitus †
Musculoskeletal and Connective Tissue	Arthralgia, back pain, myositis, musculoskeletal pain, arthritis, pain in extremity, tenosynovitis †
Nervous system	Headache, dizziness, dysgeusia, epilepsy †, lethargy †, Guillain-Barré syndrome†, peripheral neuropathy†, myasthenic syndrome †, encephalitis †, myelitis†
Psychiatric disorders	Insomnia †
Renal and urinary	Nephritis †
Respiratory, Thoracic and Mediastinal	Cough, pneumonitis, dyspnoea
Skin and Subcutaneous Tissue	Pruritus*, rash*, vitiligo, dry skin, erythema, hair color change †, eczema †, alopecia †, severe skin reaction†, Steven-Johnson Syndrome†, toxic epidermal necrolysis†
Vascular Disorders	Hypertension †, vasculitis †

6.1.2 Pralatrexate

Per package insert: the most common adverse reactions (>35%) are mucositis, thrombocytopenia, nausea, and fatigue. Most common serious adverse reactions are pyrexia, mucositis, sepsis, febrile neutropenia, dehydration, dyspnea, and thrombocytopenia.

Bone Marrow Suppression

Pralatrexate can suppress bone marrow function, manifested by thrombocytopenia, neutropenia, and anemia.

Mucositis

Treatment with pralatrexate may cause mucositis.

Dermatologic Reactions

Pralatrexate has been associated with severe dermatologic reactions, which may result in death. Dermatologic reactions have been reported in clinical studies and post-marketing safety reports in patients treated with pralatrexate. Dermatologic reactions have included skin exfoliation, ulceration, and toxic epidermal necrolysis (TEN) (post-marketing reports). These reactions may be progressive and increase in severity with further treatment, and may involve skin and subcutaneous sites of known lymphoma.

Tumor Lysis Syndrome

Tumor lysis syndrome has been reported in patients with lymphoma receiving pralatrexate in post-marketing reports.

Hepatic Toxicity

Hepatic toxicity and liver function test abnormalities have been observed after pralatrexate administration. Persistent liver function test abnormalities may be indicators of liver toxicity.

Risk of Increased Toxicity in the Presence of Impaired Renal Function

Patients with moderate to severe renal function impairment may be at greater risk for increased exposure and toxicity. Serious adverse drug reactions including TEN (post-marketing reports) and mucositis were reported in patients with end stage renal disease (ESRD) undergoing dialysis who were administered FOLOTYN therapy.

Pregnancy and Breastfeeding

Pralatrexate can cause fetal harm when administered to a pregnant woman. Pralatrexate was embryotoxic and fetotoxic in rats and rabbits.

6.2 Dose Delay/ Modification - General instructions

If pembrolizumab administration is held for toxicity, and the toxicity is most likely attributed to pembrolizumab and not attributed to pralatrexate, administration of pralatrexate may continue.

If pralatrexate administration is held for toxicity, and the toxicity is most likely attributed to pralatrexate and not attributed to pembrolizumab, administration of pembrolizumab may continue.

In the event that attribution of a treatment-emergent toxicity is unclear, but is at least possibly related to both study medications, both drugs should be delayed/modified according to the most conservative dose delay criteria. The most conservative dose delay criteria should be observed for any particular AEs called out in the dose delay/modification tables (Tables 6.3, 6.4.1, 6.4.2, or 6.4.3) or according to the general “all other IrAE” guidelines in Table 6.3 for unspecified immune-related AEs or the “all other pralatrexate-related” AE guidelines in Table 6.4.3 for non-immune related AEs.

6.3 Dose Delay/ Modification Guidelines for Pembrolizumab-associated Adverse Events

- Toxicities will be graded using the [NCI CTCAE Version 5.0](#).
- Baseline values are from the last values obtained prior to treatment.

AEs associated with pembrolizumab exposure may represent an immunologic etiology. These immune-related AEs (irAEs) may occur shortly after the first dose or several months after the last dose of pembrolizumab treatment and may affect more than one body system simultaneously. Therefore, early recognition and initiation of treatment is critical to reduce complications. Based on existing clinical study data, most irAEs were reversible and could be managed with interruptions of pembrolizumab, administration of corticosteroids and/or other supportive care. For suspected irAEs, ensure adequate evaluation to confirm etiology or exclude other causes. Additional procedures or tests such as bronchoscopy, endoscopy, skin biopsy may be included as part of the evaluation. Based on the severity of irAEs, withhold or permanently discontinue pembrolizumab and administer corticosteroids. Dose modification and toxicity management guidelines for irAEs associated with pembrolizumab are provided in Table 6.3.

Table 6.3 Dose Modification and toxicity management for irAEs typically associated with pembrolizumab

General instructions:

1. Corticosteroid taper should be initiated upon AE improving to Grade 1 or less and continue to taper over at least 4 weeks.
2. For situations represented in Table 6.3 where pembrolizumab has been withheld, pembrolizumab can be resumed after AE has been reduced to Grade 1 or 0 and corticosteroid has been tapered. Pembrolizumab should be permanently discontinued if AE does not resolve within 12 weeks of last dose or corticosteroids cannot be reduced to ≤ 10 mg prednisone or equivalent per day within 12 weeks.
3. For situations represented in Table 6.3 where pralatrexate has been withheld, pralatrexate can be resumed at prior dose after AE improves to grade 1 or 0. If the investigator feels that the AE was related to pralatrexate, the pralatrexate dose can be reduced by one level after discussion with the overall study PI.

Exceptions:

- For patients who develop severe renal impairment (eGFR or CrCl 15 to < 30 mL/min/1.73m 2) while on treatment with pralatrexate at the 30 mg/m 2 dose level, the dose of pralatrexate upon recovery will be reduced to 15 mg/m 2 .
- For patients who develop severe renal impairment (eGFR or CrCl 15 to < 30 mL/min/1.73m 2) while on treatment with pralatrexate at the 20 mg/m 2 dose level or lower, pralatrexate will be permanently discontinued.
- 4. For severe and life-threatening irAEs, IV corticosteroid should be initiated first followed by oral steroid. Other immunosuppressive treatment should be initiated if irAEs cannot be controlled by corticosteroids.

Immune-related AEs	Toxicity grade or conditions (CTCAE v5.0)	Action taken to pembrolizumab and/or pralatrexate	irAE management with corticosteroid and/or other therapies	Monitor and follow-up
Pneumonitis	Grade 2	
 Withhold pembrolizumab Consider holding pralatrexate 	
 Administer corticosteroids (initial dose of 1-2 mg/kg prednisone or equivalent) followed by taper Add prophylactic antibiotics for opportunistic infections 	
 Monitor participants for signs and symptoms of pneumonitis Evaluate participants with suspected pneumonitis with radiographic imaging and initiate corticosteroid treatment
	Grade 3 or 4, or recurrent Grade 2	
 Permanently discontinue pembrolizumab Hold pralatrexate 		
Diarrhea / Colitis	Grade 2 or 3	
 Withhold pembrolizumab Hold pralatrexate 	
 Administer corticosteroids (initial dose of 1-2 mg/kg prednisone or equivalent) followed by taper 	
 Monitor participants for signs and symptoms of enterocolitis (ie, diarrhea, abdominal pain, blood or mucus in stool with or without fever) and of bowel perforation (ie, peritoneal signs and ileus). Participants with \ge Grade 2 diarrhea suspecting colitis should consider GI consultation and performing endoscopy to rule out colitis. Participants with diarrhea/colitis should be advised to drink liberal quantities of clear fluids. If sufficient oral fluid intake is not feasible, fluid and electrolytes should be substituted via IV infusion.
	Grade 4, or recurrent Grade 3	
 Permanently discontinue pembrolizumab Hold pralatrexate 		
AST / ALT elevation or Increased bilirubin	Grade 2	
 Withhold pembrolizumab Hold pralatrexate 	
 Administer corticosteroids (initial dose of 0.5- 1 mg/kg prednisone or equivalent) followed by taper 	
 Monitor with liver function tests (consider weekly or more frequently until liver enzyme value returned to baseline or is stable)
	Grade 3 or 4	
 Permanently discontinue pembrolizumab Hold pralatrexate 	
 Administer corticosteroids (initial dose of 1-2 mg/kg prednisone or equivalent) followed by taper 	

Type 1 diabetes mellitus (T1DM) or Hyperglycemia	Newly onset T1DM or Grade 3 or 4 hyperglycemia associated with evidence of β -cell failure	
 Withhold pembrolizumab 	
 Initiate insulin replacement therapy for participants with T1DM Administer anti-hyperglycemic in participants with hyperglycemia 	
 Monitor participants for hyperglycemia or other signs and symptoms of diabetes.
Hypophysitis	Grade 2	
 Withhold pembrolizumab 	
 Administer corticosteroids and initiate hormonal replacements as clinically indicated. 	
 Monitor for signs and symptoms of hypophysitis (including hypopituitarism and adrenal insufficiency)
	Grade 3 or 4	
 Withhold or permanently discontinue pembrolizumab¹ 		
Hyperthyroidism	Grade 2	Continue pembrolizumab	
 Treat with non-selective beta-blockers (eg, propranolol) or thionamides as appropriate 	
 Monitor for signs and symptoms of thyroid disorders.
	Grade 3 or 4	Withhold or permanently discontinue pembrolizumab ¹		
Hypothyroidism	Grade 2, 3, or 4	Continue pembrolizumab	
 Initiate thyroid replacement hormones (eg, levothyroxine or liothyroinine) per standard of care 	
 Monitor for signs and symptoms of thyroid disorders.
Nephritis and Renal dysfunction	Grade 2	
 Withhold pembrolizumab Hold pralatrexate 	
 Administer corticosteroids (prednisone 1-2 mg/kg or equivalent) followed by taper. 	
 Monitor changes of renal function
	Grade 3	
 Permanently discontinue pembrolizumab Hold pralatrexate 		
	Grade 4	
 Permanently discontinue pembrolizumab and pralatrexate 		
Neurological Toxicities	Grade 2	
 Withhold pembrolizumab Hold pralatrexate 	
 Based on severity of AE administer corticosteroids 	
 Ensure adequate evaluation to confirm etiology and/or exclude other causes
	Grade 3 or 4	
 Permanently discontinue pembrolizumab Hold pralatrexate 		

		If the neurological toxicity is felt to be due to pembrolizumab and not pralatrexate, resumption of pralatrexate may be considered in consultation with the study PI.		
Myocarditis	Grade 1	
 Withhold pembrolizumab Hold pralatrexate 	
 Based on severity of AE administer corticosteroids 	
 Ensure adequate evaluation to confirm etiology and/or exclude other causes
	Grade 2, 3 or 4	
 Permanently discontinue pembrolizumab Hold pralatrexate 		
Exfoliative Dermatological Conditions	Suspected SJS, TEN, or DRESS	
 Withhold pembrolizumab Hold pralatrexate 	
 Based on type and severity of AE administer corticosteroids 	
 Ensure adequate evaluation to confirm etiology and/or exclude other causes
	Confirmed SJS, TEN, or DRESS	
 Permanently discontinue pembrolizumab and pralatrexate 		
All other immune-related AEs	Intolerable/persistent Grade 2	Withhold pembrolizumab	
 Based on type and severity of AE administer corticosteroids 	
 Ensure adequate evaluation to confirm etiology and/or exclude other causes
	Grade 3	Withhold or discontinue pembrolizumab based on the type of event. Events that require discontinuation include, but are not limited to: encephalitis and other clinically important irAEs		
	Grade 4 or recurrent Grade 3	Permanently discontinue pembrolizumab		

1. Withhold or permanently discontinue pembrolizumab is at the discretion of the investigator or treating physician.
 
NOTE:
 
For participants with Grade 3 or 4 immune-related endocrinopathy where withhold of pembrolizumab is required, pembrolizumab may be resumed when AE resolves to ≤ Grade 2 and is controlled with hormonal replacement therapy or achieved metabolic control (in case of T1DM).
				

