Grade 4	Permanently discontinue pralatrexate Hold pembrolizumab	If not probably or definitely related to pembrolizumab, pembrolizumab resumption can be considered in discussion with Study PI

Table 6.4.2 Dose Modifications for Hematologic Toxicities

Blood Count on Day of Treatment	Duration of Toxicity	Action	Dose Upon Restart
Platelet ≤25,000/µL	1 week	Omit pralatrexate dose Hold pembrolizumab	Continue prior pralatrexate dose Resume pembrolizumab
	2 weeks	Omit pralatrexate dose Hold pembrolizumab	reduce pralatrexate by one dose level Resume pembrolizumab
	3 weeks	Permanently stop pralatrexate Hold pembrolizumab	Pembrolizumab resumption can be considered in discussion with Study PI
ANC 500-1,000/µL with fever OR ANC <500/µL	1 week	Omit pralatrexate dose, give GCSF support Hold pembrolizumab	Continue prior pralatrexate dose with GCSF support Resume pembrolizumab
	2 weeks or recurrence	Omit pralatrexate dose, give GCSF support Hold pembrolizumab	reduce pralatrexate by one dose level with GCSF support Resume pembrolizumab
	3 weeks or 2 nd recurrence	Permanently stop pralatrexate Hold pembrolizumab	Pembrolizumab resumption can be considered in discussion with Study PI

ANC= absolute neutrophil count, GCSF=granulocyte colony stimulating factor, GMCSF= granulocyte macrophage colony stimulating factor.

Table 6.4.3 Dose Modifications for all Other Pralatrexate-Related Toxicities

Toxicity Grade On Day of Treatment	Action	Dose Upon Recovery to ≤Grade 1
Grade 3	Omit pralatrexate dose	reduce pralatrexate by one dose level
Grade 4	Permanently stop pralatrexate therapy	---

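### After a grade 4 bowel or liver event first managed under Table 6.3 and then attributed to pralatrexate, general instruction 3 permits re-dosing where Table 6.4.3 directs a permanent stop

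*Combined protocol and SAP*

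**What the plan says.** Table 6.3 in Section 6.3 covers immune-related events typical of pembrolizumab. In its diarrhea/colitis rows, pralatrexate is held at grade 2 or 3 and again at "Grade 4, or recurrent Grade 3". In the row "AST / ALT elevation or Increased bilirubin", pralatrexate is held at grade 2 and at grade 3 or 4. None of these rows stops pralatrexate for good.

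General instruction 3 to that table sets the restart rule: "pralatrexate can be resumed at prior dose after AE improves to grade 1 or 0". A second sentence adds an option: "If the investigator feels that the AE was related to pralatrexate, the pralatrexate dose can be reduced by one level after discussion". The party to be consulted is the study PI. Its only listed exceptions concern severe renal impairment.

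Table 6.4.3 in Section 6.4 covers pralatrexate-related toxicities other than mucositis and hematologic events. Its trigger column is headed "Toxicity Grade On Day of Treatment". At grade 3 the dose is omitted and pralatrexate comes back one level lower on recovery to grade 1 or less. At grade 4 the action is "Permanently stop pralatrexate therapy".

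Section 6.2 addresses attribution. Where it is unclear and both drugs may be involved, "both drugs should be delayed/modified according to the most conservative dose delay criteria". Where pralatrexate is held and "the toxicity is most likely attributed to pralatrexate and not attributed to pembrolizumab, administration of pembrolizumab may continue"; that sentence gives no pralatrexate dose rule.

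**The concern.** Instruction 3 provides, inside Table 6.3, for an event that the investigator considers related to pralatrexate. It gives that event a weaker rule than Table 6.4.3 does, with no limit by grade and no pointer to Table 6.4.3. At grade 4, one instruction permits what the other rules out.

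At stake is the safety and uniformity of re-dosing. Two sites could treat the same patient differently after a grade 4 liver or bowel event attributed to pralatrexate, one restarting and one stopping for good. The scenario is not far-fetched: Section 6.1.2 lists hepatic toxicity as a pralatrexate effect, and Section 6.3 applies to suspected immune-related events whose cause is still being evaluated. No sample size, error rate or response estimate depends on this point.

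**Working it through.** The plan states no figure here, so the check compares the rules and then asks whether the other limits in the protocol close the gap.

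**Rules side by side, for an event present on a pralatrexate dosing day and attributed to pralatrexate rather than pembrolizumab**

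| Grade on dosing day | Table 6.3 with instruction 3 | Table 6.4.3 |
|---|---|---|
| 4 | Hold; on recovery to grade 0 or 1, restart at the prior dose or, optionally, one level lower | Permanent stop |
| 3 | Hold; on recovery, restart at the prior dose or, optionally, one level lower | Omit; on recovery, one level lower |

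**Does Section 6.2 settle it?** Its most-conservative paragraph opens with unclear attribution and possible involvement of both drugs. Such events fall under the stricter table. For attribution to pralatrexate alone, 6.2 says only that pembrolizumab may go on.

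**Do the other limits close it?** The inputs are 21-day cycles with pralatrexate on days 1 and 8 (Section 5.3); discontinuation of pralatrexate after more than 28 days without it (Section 6.4); no new cycle while grade 3 or higher pralatrexate-related toxicity is ongoing (Section 5.4); and unacceptable toxicity, which for a non-hematologic grade 4 event means no resolution to grade 1 or less within 7 days, with some exceptions (Section 11.2). Study days of dosing without delay are 1, 8, 22, 29 and 43. The examples assume that the event begins on the dosing day on which it is graded.

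- *Grade 4 on study day 8.* The last dose was day 1. Resolution by 8 + 7 = day 15 keeps the event outside the 11.2 definition. The next scheduled dose is day 22, a gap of 22 − 1 = 21 days, within 28.
- *Grade 4 on study day 22.* The last dose was day 8. Cycle 2 cannot start while the toxicity is ongoing. With resolution by 22 + 7 = day 29, dosing on day 29 gives a gap of 29 − 8 = 21 days. Section 6.4 calls for re-evaluation at least weekly during a delay, so day 36 is also open: 36 − 8 = 28 days, which is not more than 28.

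The limits therefore do not close the gap for grade 4 events that resolve quickly.

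**Pralatrexate per cycle on restart** (dose level × 2; one level down is 30 to 20, or 20 to 15 mg/m²)

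| Grade and prior level | Instruction 3: prior dose, or one level lower | Table 6.4.3 |
|---|---|---|
| 4, 30 mg/m² | 60 or 40 mg/m² | 0 |
| 4, 20 mg/m² | 40 or 30 mg/m² | 0 |
| 3, 30 mg/m² | 60 or 40 mg/m² | 40 mg/m² |
| 3, 20 mg/m² | 40 or 30 mg/m² | 30 mg/m² |

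At grade 3 the largest ratios are 60/40 = 1.50 and 40/30 = 1.33. If the site takes the optional reduction, the two rules coincide.

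**The case against.** The best defense is scope. Table 6.3 is for immune-related events; Section 7.3.1 requires that such an event have no clear alternate cause; and Section 5.13.1 restricts systemic steroids, which the bowel and liver rows direct, largely to events of suspected immunologic origin. On that view an event due to pralatrexate alone belongs to Table 6.4.3 from the start. Applying Table 6.3 to it even gives an odd result at grade 4: pembrolizumab, the drug not blamed, is ended, and pralatrexate, the drug blamed, is restarted. The last sentence of Section 6.2 can also be read as a sorting rule that sends non-immune events to Table 6.4.3.

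This narrows the gap but does not remove it. Instruction 3 itself contemplates an event related to pralatrexate within Table 6.3 and sets its own contrary rule. The sorting sentence in 6.2 sits in the paragraph on unclear attribution. Table 6.3 also states a pralatrexate stop where one is meant, for grade 4 nephritis and for confirmed severe exfoliative skin reactions, and it does not do so in the bowel and liver rows.

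A reader might infer more than the text supports in three ways.

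- *That the tables conflict for every grade 3 or 4 bowel or liver event.* They do not; shared or unclear attribution is covered by 6.2.
- *That any grade 4 event triggers the stop in Table 6.4.3.* Its trigger is the grade on the day of treatment, so an event that peaks and recovers between dosing days does not clearly meet it.
- *That a site cannot comply with both rules.* Instruction 3 is permissive, so a site that takes the stricter action satisfies both. The fault is the permission, not an obligation to re-dose.

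**Conclusion.** The inconsistency is real and narrow. It concerns a grade 4 diarrhea/colitis or AST/ALT/bilirubin event that is present on a pralatrexate dosing day, is first managed under Table 6.3, and is then attributed to pralatrexate rather than pembrolizumab. For that patient the protocol both permits restart and directs a permanent stop. The grade 3 difference is minor.

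The number of patients cannot be estimated, because the documents give no rate for such events; it is likely small. Recovery to grade 0 or 1, the cycle criteria in 5.4, the 28-day limit and removal for unacceptable toxicity under 5.10 all restrict re-dosing. If 5.10 is read with the 11.2 definition, which it does not cite, most grade 4 events lasting beyond 7 days would end therapy whichever table is used. What remains is mainly grade 4 events that resolve within 7 days. The dose figures describe what the rules allow for such a patient, not an expected average. The point merits correction because the text as written permits re-dosing after a grade 4 event attributed to the drug.

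**What to change.** Replace the second sentence of general instruction 3 for grade 3 and 4 events with wording such as: *If a grade 3 or 4 AE present on a day of treatment is attributed to pralatrexate, Table 6.4.3 governs pralatrexate (grade 3: reduce by one level on recovery to grade 1 or less; grade 4: permanently stop); resumption at the prior dose after a grade 3 or 4 AE applies only if the AE is judged not related to pralatrexate.*

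Keep the present wording for grade 2, for which Table 6.4.3 has no row, and keep the renal exceptions.

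Two additions are optional: a pointer to Table 6.4.3 in the bowel and liver rows, and a clause in Section 6.2 saying that the most conservative rule includes the restart dose and that pralatrexate follows Tables 6.4.1 to 6.4.3 when the event is attributed to it alone.

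The cost is a short amendment, slightly less investigator discretion and slightly less pralatrexate exposure in a few patients.
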